Despite these suggested therapeutic benefits of combined thermal ablation and embolization techniques, little is known about the prognostic effects of MWA + TAE in early-stage HCC. To our knowledge, no RCTs have compared the combination therapy (MWA + TAE) with monotherapy (MWA alone) in this selective cohort. The efficacy of MWA in combination with TAE as a prophylactic treatment to reduce recurrence in HCC patients with a small tumor burden is unknown. Moreover, the optimal protocol and timing for MWA combined with TAE as a treatment for early stage HCC has yet to be determined. For all of these reasons, RCTs are required to examine the feasibility as well as the possible therapeutic and/or survival benefits of combination MWA + TAE in selected patients with early-stage HCC.

STUDY DESIGN

Objective

This single-center, prospective RCT is designed to compare the outcomes and clinicopathologic results of blunt transarterial embolization (TAE) and microwave ablation (MWA) combination therapy with MWA monotherapy for the treatment of early (stages 0 and A) hepatocellular carcinoma (HCC). The primary aim of this study is to test the following hypothesis: 2-year intrahepatic disease-free survival does not differ between patients receiving the experimental therapy (MWA + TAE) and patients receiving the standard therapy (MWA alone) as treatment for early-stage HCC. Secondary aims are: 1) to determine the clinical feasibility of TAE + MWA in HCC patients with a small tumor burden using patient demographics and disease characteristic data and 2) to determine the effect of TAE on radiographic tumor characteristics in this patient cohort.

The primary outcome is 2-year intrahepatic disease-free survival, which is measured from time of randomization and is defined as the absence of local or regional recurrence of HCC as determined by diagnostic imaging. *Local recurrence* is defined as an enhancing lesion contiguous with the ablation zone that is present on subsequent imaging but was not present on the initial postablation scan. *Regional recurrence* is defined as hepatic recurrence that is not adjacent to the ablation site.

Secondary outcome measures include:

- Patient and disease characteristics (Table 1)
- 1-year, 2-year, 3-year, and 5-year overall survival;
- 1-year, 3-year, and 5-year intrahepatic disease-free survival;
- Number of TAE procedures required (for multilobar lesions or repeat effect)

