According to a computer-generated variable size blocked randomization method, eligible patients will be allocated on a 1:1 basis to receive the experimental therapy (MWA + TAE) and standard therapy (MWA alone), respectively. The nature of the treatments and their possible adverse effects preclude the use of double-blind and double dummy techniques. In patients randomized to receive the experimental therapy, TAE treatments will be initiated within one week of randomization, then followed by MWA within 4 to 6 weeks after reviewing radiological scans from TAE. MWA will be performed 4 to 6 weeks following randomization in MWA standard therapy groups. Treatment may be discontinued if any exclusion criteria develop in the patient or at the patient's request.

Sample Size

Power calculations are based upon expected 2-year survival rates. The main endpoint is 2-year intrahepatic disease-free survival, measured from the time of randomization which is measured from time of randomization and is defined as the absence of local or regional recurrence of HCC as determined by diagnostic imaging. Considering an estimated 80% and 90% intrahepatic disease-free survival at 2 years of follow-up for patients receiving MWA alone and MWA + TAE combination therapy, respectively, a sample size of 92 patients is required to detect a clinically meaningful 10% absolute difference in 2-year peritoneal disease-free survival with MWA + TAE with a minimum of 95% power and a 2-sided $\alpha = .05$. To account for a 5–10% withdrawal rate (following intraoperative detection of vascular invasion or extrahepatic metastasis, etc.), a sample size of 100 patients is required (50 patients per arm). If the rate of patient enrollment is suboptimal, a covariate adaptive randomization method will be used to allocate patients in a 2:1 ratio to receive experimental therapy (MWA + TAE) and standard therapy (MWA alone), respectively, which would result in an overall sample size of 83 patients.

Clinical Procedures

Preprocedural Strategy

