All operative MWAs will be performed in a laparoscopic or robot-assisted laparoscopic setting by one of four hepatobiliary surgeons with extensive experience with intraoperative US guidance and hepatic ablation ([name]). Care will be taken to create ample distance between the microwave near-field and any adjacent structures (diaphragm/heart, stomach/esophagus, colon, duodenum, gallbladder) by mobilization of the liver. All ablations will be guided by intraoperative ultrasound (BK Medical A/S, Herlev, Denmark) with care taken to allow for complete tumor treatment while preserving adequate distance between the microwave near-field and adjacent intrahepatic structures (portal pedicles, hepatic veins). Ablations will be performed with a 2.45-GHz generator with a 1.8-mm-diameter transcutaneous antenna (Acculis pMTA Accu2i; AngioDynamics Inc., Denmead, Hampshire, UK).

Operative variables will be recorded per patient, and individual ablation characteristics including tumor location by hepatic segment, proximity to a portal pedicle, number of applications, power settings, and ablation duration will be recorded for each individual tumor. A clearly demarcated zone of color flow Doppler activity will be visualized within 30 s of initiating the ablation to assure that the target is within the microwave ablation zone. Patients will be observed carefully, and analgesia will be administered per standard protocol if necessary.

Postprocedural Strategy

Division-specific standard guidelines will be applied to the postoperative care of patients included in this study. Postoperative complications will be recorded and treated symptomatically. All patients will be closely followed up for disease progression with clinical and laboratory examinations 4–6 weeks after ablation/TAE procedures, then every 3 months for the first 2 years. At 4–6 weeks following TAE +/- MWA procedures, tumors will be assessed radiographically and characteristics will be reported according to the LI-RADS criteria and guidelines. Imaging techniques will then be performed every 3 months during the first 2 years postoperative and every 6 months afterward. In addition, AFP levels will be obtained every 3 months during the first 2 years postoperative and every 6 months afterward.

Data Collection

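### Surveillance scans are timed from surgery but the 2-year endpoint runs from randomisation, so no scan is scheduled at 2 years; the effect is small and its direction depends on unresolved wording

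*Combined protocol and SAP*

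**What the plan says.** **Endpoint clock.** Under Objective: "The primary outcome is 2-year intrahepatic disease-free survival, which is measured from time of randomization". The event is read from scans, as the endpoint is the "absence of local or regional recurrence of HCC as determined by diagnostic imaging". The Sample Size and Definitions sections use the same origin.

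**Scan clock.** Under Postprocedural Strategy: "At 4–6 weeks following TAE +/- MWA procedures, tumors will be assessed radiographically". After that: "Imaging techniques will then be performed every 3 months during the first 2 years postoperative and every 6 months afterward". The secondary outcome list likewise gives a scan 4-6 weeks after ablation and then 3-monthly scans. No visit windows are given.

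**Time from randomisation to surgery.** For controls: "MWA will be performed 4 to 6 weeks following randomization in MWA standard therapy groups". For the combination arm, "TAE treatments will be initiated within one week of randomization", "then followed by MWA within 4 to 6 weeks after reviewing radiological scans from TAE".

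**Analysis.** Kaplan-Meier and log-rank by intention to treat. The Statistical Analysis section does not address recurrences that are known only to lie between two scans.

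**The concern.** A recurrence is dated by the scan that shows it. If no scan is due at 24 months from randomisation, the Kaplan-Meier estimate at 24 months reflects disease status at the last scan before that date. Recurrences between that scan and the 2-year mark are missed, so the 2-year rate reads too high.

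If that last scan falls at the same time in both arms, the comparison is unaffected. If it does not, the arms are read at different times and a difference can appear without any treatment effect. Whether this happens depends on two things the text leaves open: when MWA takes place in the combination arm, and which event the 3-monthly scans count from. At stake are the accuracy of the headline 2-year difference and whether two readers of this protocol would build the same scan calendar.

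**Working it through.** The plan gives no scan calendar in weeks from randomisation, so there is no figure of its own to reproduce. I built the calendar from its stated intervals.

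**Inputs**
- 2 years = 104.4 weeks; 3 months = 13.04 weeks.
- Control MWA: weeks 4-6.
- Combination MWA, earlier reading (4-6 weeks after TAE, itself in weeks 0-1): weeks 4-7.
- Combination MWA, later reading (TAE, a scan 4-6 weeks later, then a further 4-6 weeks): weeks 8-13.
- True 2-year DFS of 80% in both arms, the control rate in the Sample Size section.
- Assumed: constant recurrence hazard from randomisation, timing uniform within the stated windows, scans done on schedule.

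**Step 1: scans on either side of week 104.** Counted from surgery, scan *k* is at MWA week + 13.04*k*. Counted from the 4-6 week scan, add a further 4-6 weeks. For controls counted from surgery, 7 × 13.04 = 91.3, and adding 4 to 6 gives weeks 95.3-97.3.

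| | Counted from surgery | Counted from the 4-6 week scan |
|---|---|---|
| Control | 95-97, then 108-110 | 99-103, then 112-116 |
| Combination, earlier reading | 95-98, then 108-111 | 99-104, then 112-117 |
| Combination, later reading | 99-104, then 112-117 | 90-97, then 103-110 |

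On schedule, no control scan falls at week 104 under either count. On the later reading the combination calendar moves by typically 5-6 weeks. Counted from the 4-6 week scan, that leaves about 7 scans by 2 years instead of 8.

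If postoperative counts from TAE in the combination arm, a scan falls at weeks 104-105 (counted from the procedure) or at 95-98 and 108-111 (counted from the first scan).

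**Step 2: the 2-year rate as observed.** The hazard is -ln(0.8)/104.4 = 0.002137 per week. Observed 2-year DFS is approximately exp(-0.002137 × *L*), where *L* is the mean week of the last scan before 2 years.

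| | *L*, from surgery | DFS | *L*, from first scan | DFS |
|---|---|---|---|---|
| Control | 96.3 | 0.8140 | 101.3 | 0.8054 |
| Combination, earlier | 96.8 | 0.8131 | 101.8 | 0.8045 |
| Combination, later | 101.8 | 0.8045 | 93.8 | 0.8183 |

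Combination minus control:
- Earlier reading: -0.1 point under either count.
- Later reading, counted from surgery: 80.45 - 81.40, about -1.0 point.
- Later reading, counted from the first scan: 81.83 - 80.54, about +1.3 points.
- Every combination MWA at week 13, counted from surgery: *L* = 91.3 + 13 = 104.3, DFS 80.0%, difference -1.4 points.

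Simulation of the same schedules agrees: -1.0 and +1.3 points on the later reading. At an assumed true DFS of 60% the two differences become -1.7 and +2.3 points.

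**Step 3: the log-rank test.** I simulated 46 patients per arm (half of the plan's 92) with no treatment effect, 3,000 runs per setting, and an assumed follow-up uniform on 0-208 weeks. On the later reading the test rejected in 4.6-4.8% of runs, against 4.7-5.6% with identical schedules. No inflation is visible.

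**Step 4: common dates.** With scans at the same times from randomisation in both arms, one of them at 2 years, a true 80% reads as 80% in both and the difference due to timing is 0.

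**The case against.** The best defence is that the timings were meant to match. Delaying control MWA to weeks 4-6 makes sense if combination MWA falls at weeks 4-7, and on that reading the arms are scanned almost together. The later reading adds a post-TAE scan to a further interval. It also treats 4 weeks as a minimum, although the text says within 4 to 6 weeks, so week 8 is not a firm lower limit. This stands as far as it goes: the shift between arms is conditional. But the text does not say that alignment was intended, and it does allow the later reading.

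The effect is also small beside sampling error. With 46 per arm the standard error of the 2-year difference is √(2 × 0.16/46) = 8.3 points at 80% in both arms, or √((0.16 + 0.09)/46) = 7.4 points at 80% and 90%. One point is about 0.12-0.14 standard errors. Kaplan-Meier and log-rank do not need a scan at exactly 2 years, and patients followed further have late recurrences counted at the next scan. This stands too, and is why the point is minor. The error is nevertheless systematic, so more patients would not remove it.

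A reader might infer more than the documents support:
- *That no patient can have a scan at 2 years.* This holds for controls on schedule. In the combination arm a scan can fall at or near week 104 on the later reading, or if the count starts at TAE.
- *That the arms are bound to be scanned at different times.* On the earlier reading they are not, to any degree that matters.
- *That a particular arm is favoured.* The sign reverses between the two ways of counting 3-monthly scans. The apparent hazard ratio also depends on the model: counting scans from surgery on the later reading, it is about 1.06 if risk starts at randomisation and 0.96-1.00 if it starts at MWA.
- *That the log-rank test is invalid.* Step 3 shows no sign of this.
- *That the overstated rate itself biases the comparison.* A detection lag common to both arms does not.

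**Conclusion.** The mismatch is real. The endpoint and the scans have different time origins, no scan is scheduled at 24 months from randomisation, and in controls none can fall there on schedule. A true 80% control rate would read about 81.4% or 80.5%.

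A spurious difference between arms arises on the later reading of MWA timing: about -1.0 or +1.3 points, depending on the scan count, and -1.4 if every combination MWA fell at week 13 with scans counted from surgery. That is roughly a tenth to a seventh of the 10-point target. On the earlier reading it is negligible. These sizes rest on a constant hazard, equal true rates and on-schedule scanning, and would be larger if recurrence were commoner.

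Severity is minor. It is still worth correcting, because the open wording determines both the size and the direction of the error in the primary quantity.

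**What to change.** 1. Schedule surveillance scans at the same times from randomisation in both arms, with stated windows and one scan at 24 months.
2. Keep the initial post-ablation scan timed from the procedure, because it is the baseline for judging local recurrence.
3. Keep the Kaplan-Meier and log-rank analysis.
4. If surgical timing is retained instead, state whether 3-monthly scans count from the procedure or from the 4-6 week scan, and prespecify a sensitivity analysis that treats recurrence times as interval-censored.
5. The sponsor should reconcile the passages on the combination-arm MWA interval and on which procedure postoperative counts from. I propose no clinical timing.

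**Cost.** Mainly an amendment to the imaging schedule and its windows. On the later MWA reading, an early scan timed from randomisation (week 13, for example) may fall close to or before the post-ablation baseline scan. The early visits would then need aligning, and one scan might have to be added or merged.

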All parameters will be prospectively collected. The study will be approved by the Internal Review Board of Carolinas Medical Center, and informed consent will be obtained from all patients prior to study participation. All hepatocellular carcinomas will be classified according to the TNM criteria of the American Joint Commission on Cancer (AJCC) 2010 Cancer System. A comprehensive medical history will be obtained from each patient and supplemented by clinical notes. Pre-, intra-, and postoperative variables (Table 1) and clinical outcomes will be recorded in an electronic database. Toxicity induced by TAE and or MWA will be graded according to the [Common Terminology Criteria for Adverse Events - CTCAE v5.0](#) (Slated for release in October 2015; v4.3 available at <http://evs.nci.nih.gov/ftp1/CTCAE/About.html>).

Table 1. Variables for analysis

Patient characteristics	age, sex, viral hepatitis status, nicotine use, alcohol use, drug use, hypertension, obesity, diabetes mellitus, general conditions, prior therapy, underlying disease status as determined by Child-Pugh and MELD score
Preoperative imaging	presence of cirrhosis; tumor size, location and number
Intraoperative findings	surgeon performing procedures, proximity of tumor to portal pedicle, number of TAE applications, number of MWA applications, power settings, ablation duration (per application and per tumor), pathology from random liver biopsy
Postoperative data	Tumor radiology, length of stay, 30- and 90-day readmission, wound infection, postoperative complications (encephalopathy, liver failure, ascites, upper GI bleeding), postoperative Δ MELD score
Tumor characteristics	BCLC classification, Okuda stage, AJCC clinical tumor stage, venous infiltration, lymphatic infiltration
Laboratory data	α -fetoprotein (AFP) level, Hb, leukocytes, thrombocytes, serum proteins, albumin, bilirubin, γ -GT, ASAT, creatinine, INR, alkaline phosphatase

Abbreviations: MELD, Model for End-Stage Liver Disease; TAE, transarterial chemoembolization; MWA, microwave ablation; GI, gastrointestinal; BCLC, Barcelona Clinic Liver Cancer; AJCC, American Joint Committee on Cancer; Hb, hemoglobin; γ -GT, gamma-glutamyl transpeptidase; ASAT, aspartate amino transferase; INR, international normalized ratio.

Definitions

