Patients alive at the time of analysis will be censored at the last follow-up examination or at liver transplantation. Univariate analyses will be performed using the log-rank test of equality for categorical variables and the chi-square test with Cox proportional hazard model for continuous variables to identify clinical variables (Child–Pugh class, Okuda class, Model for End-Stage Liver Disease (MELD) score, etiology of cirrhosis), tumor factors (extrahepatic disease, multicentric disease, tumor size, Milan criteria, AJCC tumor stage, AFP level), and treatment-related factors (TAE, complications, recurrence) predicting intrahepatic disease-free and overall survival. Survival and disease-free survival will be estimated using the Kaplan–Meier method and tested with the log-rank test following the intention-to-treat principle. Statistical analysis will be performed using SAS software (SAS Institute, Cary, NC, USA).

The analysis will be planned at a median follow-up of two years, with an interim analysis scheduled for 1 year after the first patient is enrolled or when 50% of total expected enrollment has been reached.

To improve patient selection in the future, additional exploratory analyses will be performed to identify potential prognostic factors. Table 1 details variables that will be included in a Cox proportional hazards regression model to obtain hazard ratios and 95% confidence intervals (CIs). All P values will be two-sided and a p value $< .05$ will be considered significant.

ETHICAL AND SAFETY CONSIDERATIONS

Protection of Patients

The techniques and procedures used in this study protocol are not investigational or provisional in nature; rather, they are established in the provision of care for patients of the HPB Division at Carolinas Medical Center. The therapeutic benefit of combination of TAE/MWA treatment in this patient population remains unknown and is the focus of this study. The additive risk for adverse events is expected to be equal to the individual risks of the study procedures in this protocol.

Standard Division-specific guidelines will be closely followed to ensure patient safety and clinical well-being during all procedures. Patients will be closely monitored for complications associated with MWA and TAE, including wound complications, hematologic toxicities, and others.

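### The exploratory Cox model represents TAE by a post-randomization count of applications and omits the randomized arm, so its TAE hazard ratio is not the arm effect

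*Combined protocol and SAP*

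**What the plan says.** The Statistical Analysis section compares the arms by Kaplan–Meier curves "tested with the log-rank test following the intention-to-treat principle". It then says that "additional exploratory analyses will be performed to identify potential prognostic factors", and for these "Table 1 details variables that will be included in a Cox proportional hazards regression model to obtain hazard ratios" with 95% confidence intervals. Two-sided P < .05 counts as significant.

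Table 1 (Data Collection) has no row for the randomized arm. Its row of intraoperative findings contains "number of TAE applications, number of MWA applications, power settings, ablation duration (per application and per tumor". Its row of preoperative imaging contains "presence of cirrhosis; tumor size, location and number", and other rows hold BCLC, Okuda and AJCC stage. The univariate analyses do name TAE as a treatment-related factor, but they do not say whether it is coded as allocation, receipt or count.

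The secondary outcomes under Objective include "Number of TAE procedures required (for multilobar lesions or repeat effect", so the plan itself expects the amount of TAE to depend on disease extent and on what happens after the first treatment. Under Procedural Strategy, "power settings, and ablation duration will be recorded for each individual tumor".

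**The concern.** The randomized arm is fixed at time zero and balanced by design. The number of TAE applications is neither. It separates the arms (0 against 1 or more) and also ranks combination patients by disease extent and by repeat treatment. A hazard ratio per application therefore mixes allocation with patient characteristics that may themselves predict recurrence.

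This is the only analysis for which the plan expressly promises hazard ratios with confidence intervals, so readers are likely to take its TAE line as the treatment effect. Its stated use is to guide future patient selection, so a distorted tumor-number hazard ratio matters too.

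**Working it through.** **Plan figures.** The plan gives no hazard ratio to reproduce. From its 2-year intrahepatic disease-free survival of 80% and 90% (Sample Size), under proportional hazards, the arm hazard ratio is ln(0.90)/ln(0.80) = 0.105/0.223 = 0.47. With 100 patients allocated 1:1, expected 2-year events are 50 × 0.20 + 50 × 0.10 = 15.

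**Assumptions not in the documents.** Set A: 60/25/15% of patients have 1/2/3 tumors, the hazard ratio per extra tumor is 1.5 or 2.0, and the chance that an extra tumor adds an application is 0.2, 0.5 or 0.8. Set B: 70/20/10%, hazard ratio 1.5 per extra tumor, chance 0.2 to 1.0. In both, any TAE benefit is the same whatever the number of applications. Large simulated samples (200,000 patients per scenario in A, 60,000 in B) show what each Cox model estimates, apart from small-trial noise.

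**Step 1. TAE has no effect (set A).**

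| Model | Hazard ratio for the treatment term |
|---|---|
| Arm + tumor number | 0.99 to 1.01 |
| Count alone | 1.08 to 1.25 |
| Count + tumor number | 1.00 to 1.01 |

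Tumor number removes the bias if it stays in the model. The plan does not guarantee that. Table 1 holds about 51 terms (13 + 4 + 7 + 10 + 5 + 12 by row, counting ablation duration once) against about 15 events, or 15/51 = 0.3 events per term. They cannot all be fitted, and no selection rule is given.

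**Step 2. TAE works, true arm hazard ratio 0.47.**
- Set A, hazard ratio 1.5 per extra tumor, chance 0.2: arm + tumor number gives 0.47. Count + tumor number gives 0.56 per application, and the tumor-number hazard ratio moves from 1.50 to 1.55.
- Set B: count + tumor number gives 0.55 to 0.67, against 0.47 to 0.48 for the arm. The tumor-number hazard ratio can rise from 1.5 to about 1.7.

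The reason is that a term linear in the count is being fitted to a step. A value of 0.56 per application implies 0.56² = 0.31 for two applications and 0.56³ = 0.18 for three, while the simulated truth is 0.47 for all. Patients with more tumors are credited with too much benefit, and the tumor-number term rises to compensate.

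**Step 3. TAE repeated for poor response.** Set B was extended with 30% poor responders (hazard ratio 2), of whom 50% have TAE repeated, against 10% of the others. Count + tumor number gives 1.04 to 1.05 under no effect, a small bias. With a true arm hazard ratio of about 0.47, it gives about 0.65 to 0.74.

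**Step 4. Arm and count together.** In the setting of step 3, arm + count + tumor number gives an arm hazard ratio of 0.72 to 0.79 when the truth is 1, and 0.35 to 0.38 when the truth is about 0.47. Holding the count fixed conditions on a consequence of allocation, so keeping both terms is not a remedy.

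**The case against.** The strongest reply is that the model is exploratory and prognostic. The arm comparison belongs to the intention-to-treat log-rank test, and nothing here touches it. That stands, and it limits the weight of the point.

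A reader might infer that the TAE hazard ratio is simply confounded by tumor burden. The documents do not support that, because Table 1 also lists tumor number, size, location and stage, and step 1 shows that tumor number removes the bias under no effect. In simulated 100-patient trials with one application per tumor and hazard proportional to tumor number, false findings of harm were 14% for the count alone but 1.7% with tumor number included. Detection of a true 0.47 was 21% with the arm, 9% with the count alone and 17% with count plus tumor number. The link to burden may also be weak. Procedural Strategy has bilobar lesions treated in one session, and the plan does not define an application.

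It is also fair that 0.56 per application and 0.47 per arm are different quantities, so the gap is not all bias. Nor would one trial show it clearly. The standard error of the arm term in a 100-patient null simulation was about 0.55 on the log scale, and ln(0.56/0.47) = 0.18 is about a third of that.

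A second tempting inference is that the confidence intervals are too narrow because ablation data are held per tumor. That requires one row per tumor with ordinary standard errors, and the plan nowhere specifies this. Procedural Strategy describes recording, and the survival definitions are per patient. In null simulations, one row per patient gave 4.3% type I error (mean standard error 0.55, empirical SD 0.56), and one row per tumor gave 12.8% (0.45 against 0.62). The plan does not say how per-tumor values become one per patient. That is missing detail, not a demonstrated error.

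What survives is that the table feeding the model carries a post-randomization count and no arm, and that adjusting for tumor number does not turn the count into the arm effect when TAE works.

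**Conclusion.** The point holds for the treatment term of the exploratory Cox model.
- **TAE has no effect, tumor number in the model:** the count is close to unbiased, with a small residual (1.04 to 1.05) if TAE is repeated for poor response.
- **TAE has no effect, tumor number dropped:** the count can read about 1.1 to 1.25 and look harmful.
- **TAE works at 80% versus 90%:** the count reads about 0.55 to 0.75 per application even with tumor number included, against an arm hazard ratio of about 0.47. The tumor-number hazard ratio can be pushed from 1.5 to about 1.7.

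These sizes rest on the assumed tumor distribution, the assumed link between tumors and applications, and a benefit that does not depend on the number of applications. They are calculated for intrahepatic disease-free survival. The intention-to-treat log-rank comparison stands as written. The documents support neither the flat claim that the TAE hazard ratio is confounded by burden nor the claim that the intervals are too narrow. The correction is still worth making, because it is specific and nearly free.

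**What to change.** In Statistical Analysis, state that the Cox model includes the randomized arm as allocated and that the number of TAE applications is not a model term. Do not keep both. Report the count descriptively, in the combination arm only, and define an application.

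As a clarification, state that the patient is the unit of analysis for intrahepatic disease-free and overall survival, and name the patient-level summaries to be used (for example largest tumor, number of tumors, any tumor near a portal pedicle). Any per-tumor model of local recurrence should use variance clustered by patient (in SAS, PROC PHREG with COVS(AGGREGATE) and an ID statement for the patient).

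The cost is SAP wording and a few lines of code, with no new data. The downside is that the exploratory model no longer gives a hazard ratio per TAE application. The change does not solve the shortage of events for the number of Table 1 terms.
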